15.3 Dose Limiting Toxicities

The severity of adverse events (AEs) reviewed as potential dose-limiting toxicity (DLT) will be graded according to the CTCAE V.5.0. classification.

The occurrence of any of the following AEs during Cycle 1 (Day 1 – Day 28) will be considered a DLT, except for those AEs clearly related to disease progression or intercurrent illness.

Hematologic:

1. Grade 4 or greater hematologic toxicity (neutropenia, thrombocytopenia, or anemia)
2. Grade 3 febrile neutropenia (absolute neutrophil count [ANC] < 1000/mm³ with a single temperature of > 38.3°C (101°F) or a sustained temperature of ≥ 38°C (100.4°F) for > 1 hour)
3. Grade 3 thrombocytopenia with clinically significant bleeding

Non-hematologic:

1. Grade 2 or greater ocular toxicities leading to reduced visual acuity limiting ADL, glaucoma, retinal detachment, or retinal vascular disorder
2. NYHA class III or IV left ventricular dysfunction
3. Grade 3 or greater non-hematologic toxicity that is clinically significant with the following exceptions:
 - a. Toxicity (other than rash) that starts to resolve within 3 days of initiating optimal supportive care
 - b. Grade 3 rash that resolves to grade 1 or less within 7 days of initiating optimal supportive care
 - c. Grade 3 laboratory abnormalities that are not associated with clinical sequelae (e.g., isolated lactate dehydrogenase elevation) and resolves to Grade ≤1 within 3 days of initiating optimal supportive care
 - d. Grade 3 or 4 electrolyte laboratory abnormalities that last up to 72 hours, are not clinically complicated, and resolve spontaneously or respond to conventional medical interventions
 - e. Grade 3 or 4 amylase or lipase elevation that is not associated with symptoms or clinical manifestations of pancreatitis
 - f. Alopecia
4. Grade 4 non-hematologic toxicity, with the exception of those listed above, regardless of clinical significance or duration
5. Hy's law criteria (Grade ≥ 2 bilirubin in conjunction with grade ≥2 transaminase and without elevation of alkaline phosphatase)

In addition, clinically important or persistent toxicities not included above may also be considered a DLT at the discretion of the investigator after consultation with the SpringWorks physician.

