A DLT may require temporary interruption or permanent discontinuation of mirdametinib. Mirdametinib treatment may be restarted at the same or reduced dose after the DLT has resolved to Grade ≤ 1 . See the mirdametinib treatment modification guidelines in Table 4 below.

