15.4 Dose Modification

The Investigator may temporarily interrupt, reduce the dose or permanently discontinue one or more study drugs at their discretion due to treatment-emergent adverse event that – in the Investigator's opinion – warrants treatment modification.

The treatment with fulvestrant in Arm 1 should be modified according to the USPI (where applicable) or at the investigator's discretion.

The treatment with mirdametinib in all arms should be modified according to the guidelines provided in Table 4 and Table 5 below.

Treatment should remain interrupted until the AE has resolved to Grade ≤ 1 (of Grade ≤ 2 in the event of rash). In addition, the AE resolution to Grade 2 may be acceptable at the Investigator's discretion if same toxicity was ongoing at Grade 2 since the pre-treatment baseline). The study treatment may be re-started at the same or lower dose (see Table 4 and Table 5) if the has reached satisfactory resolution in ≤ 21 days. If the AE has taken >21 to reach satisfactory resolution, then the study treatment should be permanently discontinued, unless the Investigator has determined that re-starting the treatment has acceptable benefit-risk ratio (e.g. continued objective response or stable disease after AE resolution).

Once a dose of the study treatment has been reduced due to an AE, the subject must remain on the reduced dose for the duration of the study. One subject may have up to 2 dose reductions due to AE. Dose re-escalation after the AE resolution is not permitted.

Table 4 Guideline for Mirdametinib Dose Modification for Related Adverse Events

RELATED ADVERSE EVENTS (Worst Grade by CTCAE V. 5.0)	INTERVENTION
NEUTROPENIA (ANC DECREASE)	
Grade 3 (ANC <1.0x to 0.5x 10 ⁹ /L)	Interrupt mirdametinib until resolution to Grade ≤1, then 
 • If resolved in ≤7 days, may re-start mirdametinib at the same dose at the Investigator's discretion • If resolved in >7 days, re-start mirdametinib at the next lower dose (see Table 5).
Grade 4 (ANC <0.5x 10 ⁹ /L)	Interrupt mirdametinib until resolution to Grade ≤1, then 
 • If resolved in ≤7 days, may re-start mirdametinib at the next lower dose (see Table 5) at the Investigator's discretion • If resolved in >7 days, permanently discontinue mirdametinib.

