Grade 3 febrile neutropenia (ANC <1.0x 10 ⁹ /L with a single temperature of >38.3 degrees C [101 degrees F] or a sustained temperature of ≥38 degrees C [100.4 degrees F] for more than one hour)	Interrupt mirdametinib until complete resolution of fever and ANC resolution to Grade ≤1. After satisfactory resolution, re-start mirdametinib at the next lower dose (see Table 5).
Grade 4 febrile neutropenia (ANC and temperature criteria as listed above PLUS life-threatening signs or symptoms including septic shock, hypotension and/or acidosis)	Permanently discontinue mirdametinib.
THROMBOCYTOPENIA (PLATELET COUNT DECREASE)	
Grade 3 thrombocytopenia (Platelets <50x to ≥25x 10 ⁹ /L)	Interrupt mirdametinib until resolution to Grade ≤1, then 
 • If resolved in ≤7 days, may re-start mirdametinib at the same dose at the Investigator's discretion • If resolved in >7 days, re-start mirdametinib at the next lower dose (see Table 5).
Grade 4 thrombocytopenia (Platelets <25x 10 ⁹ /L)	Interrupt mirdametinib until resolution to Grade ≤1, then 
 • If resolved in ≤7 days, may re-start mirdametinib at the next lower dose (see Table 5) at the Investigator's discretion • If resolved in >7 days, permanently discontinue mirdametinib.
OPHTHALMOLOGICAL	

Any Grade \leq 2 event not leading to reduced visual acuity limiting ADL.	Continue mirdametinib at the same dose. Perform ophthalmologic exams at least monthly or more frequently at the Investigator's discretion until resolution to Grade \leq 1.
Any Grade 2 event reduced visual acuity limiting ADL, or any Grade \geq 3 event.	For events different from RVO or retinal detachment, interrupt mirdametinib until resolution to Grade \leq 1. Perform ophthalmologic exams at least biweekly or more frequently at the Investigator's discretion until satisfactory resolution. After resolution to Grade \leq 1, re-start mirdametinib treatment at the next lower dose (see Table 5). For Grade \geq 3 RVO or retinal detachment, permanently discontinue mirdametinib.
NEUROLOGICAL	
Grade \leq 2 seizure / convulsion, hallucination, confusion or delirium or similar events lasting >24 hours AND after ruling out other possible causes.	Interrupt mirdametinib until resolution to Grade \leq 1. After resolution to Grade \leq 1, re-start mirdametinib at the next lower dose (see Table 5).

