Grade 3 AST or ALT increase (>5.0x to 20.0x ULN if baseline was normal; >5.0x to 20.0x baseline if baseline was abnormal)	Interrupt mirdametinib until resolution to Grade ≤1 (or Grade ≤2 if the subject has liver metastases). After resolution to Grade ≤1, re-start mirdametinib at the next lower dose (see Table 5).
Grade 4 AST or ALT increase (>20.0x ULN if baseline was normal; >20.0x baseline if baseline was abnormal)	Permanently discontinue mirdametinib
Potential DILI / Hy's Law (pending clinical adjudication)	
Total bilirubin increase ≥2.0x ULN and ALT or AST increase ≥3.0x ULN	Permanently discontinue mirdametinib. If clinical adjudication confirms DILI / Hy's Law, then report DILI as SAE.
OTHER	
Grade ≥ 3 hematologic toxicities or clinically significant Grade 2 hematologic abnormalities that do not resolve within 72 hours after initiation of medical management.	Interrupt dosing, after resolution to Grade ≤ 1, restart study treatment at the next lower dose following Table 5.
Grade ≥ 3 nonhematologic toxicity that is not controlled by optimal supportive medication.	Interrupt dosing; after resolution to Grade ≤ 1 or baseline, restart study treatment at the next lower dose following Error! Reference source not found.
Other Grade 2 toxicity that is subjectively intolerable (except alopecia) and not controlled by optimal supportive medication.	Interrupt dosing; after resolution to Grade ≤ 1 or baseline, restart study treatment at the same dose.
Recurrent subjectively intolerable toxicity (at least a week interruption on 2 occasions) that is not controlled by optimal supportive medication.	Interrupt dosing; after resolution to Grade ≤ 1 or baseline, restart study treatment at the next lower dose using Error! Reference source not found. If toxicity is still intolerable, permanently discontinue study treatment (unless otherwise discussed with the Principal Investigator).

ADL=activities of daily living; LVEF=left ventricular ejection fraction

In the event a dose reduction is required, the study treatment total daily dose will be reduced as shown in Table 5:

Memorial Sloan Kettering Cancer Center
 [name]
 [name]

Table 5 Mirdametinib Dose Reduction

Dose at the time of the event	Reduced dose
2 mg BID	1 mg BID
4 mg BID	2 mg BID
6 mg BID	4 mg BID

BID = twice daily

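### Table 4's ocular rows continue dosing for some Grade 2 eye events that 15.3 counts as DLTs, and state no action for Grade 2 RVO with ADL-limiting acuity loss

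*Combined protocol and SAP*

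**What the plan says.** Section 15.3 lists as a Cycle 1 DLT: "Grade 2 or greater ocular toxicities leading to reduced visual acuity limiting ADL, glaucoma, retinal detachment, or retinal vascular disorder". The three named diagnoses stand beside ADL-limiting acuity loss as alternatives, so acuity loss is not a condition for them. The section then says "A DLT may require temporary interruption or permanent discontinuation of mirdametinib", allows restart at the same or a reduced dose after resolution to Grade ≤1, and refers the reader to Table 4.

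Table 4 (section 15.4, related adverse events) has two ophthalmological rows.

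- **Row 1** is for any Grade ≤2 "event not leading to reduced visual acuity limiting ADL". Its action is to carry on at an unchanged dose, with eye examinations at least monthly until Grade ≤1.
- **Row 2** is for Grade 2 events with ADL-limiting acuity loss and for all Grade ≥3 events. It gives two instructions. The first reads "For events different from RVO or retinal detachment, interrupt mirdametinib until resolution to Grade" ≤1, followed by restart at the next lower dose. The second is introduced by the words Grade ≥3 and reads "RVO or retinal detachment, permanently discontinue mirdametinib".

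Section 15.4 opens with a general power: "The Investigator may temporarily interrupt, reduce the dose or permanently discontinue one or more study drugs at their discretion". It also says that mirdametinib should be modified in all arms according to Tables 4 and 5.

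**The concern.** The DLT definition and the ocular rows do not fit together. An event serious enough to count against a dose level in the 3+3 decision can, under row 1, leave the affected patient on that same dose. In row 2, RVO is taken out of the interruption and is not reached by the stop until Grade 3. At Grade 2 with ADL-limiting loss, other eye events get a hold and a dose reduction, while RVO gets no instruction.

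RVO is the ocular event of most concern for this drug:

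- Section 15.6.1 says it can cause permanent loss of vision.
- Section 3.2 says the RVOs at 10 and 15 mg BID continuous came after Cycle 1. From then on the DLT text no longer applies, and Table 4 is the main event-specific guidance.
- This trial doses continuously at 4 mg BID, and Arm 2 may go to 6 and 8 mg BID. Section 4.2 reports a wide gap in safety information on continuous dosing from 2 to 10 mg/m², and equates 2 mg/m² with 4 mg BID in adults.

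**Working it through.** No published figure is at issue. The check sets the two ocular rows against the DLT definition for the three diagnoses named in 15.3, at Grade 2, with and without ADL-limiting acuity loss: 3 × 2 = 6 combinations. RVO is taken to be a retinal vascular disorder.

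| Grade 2 event | ADL-limiting acuity loss? | Cycle 1 DLT in 15.3? | Action in the ocular rows |
|---|---|---|---|
| Glaucoma | No | Yes | Row 1: same dose |
| Retinal detachment | No | Yes | Row 1: same dose |
| RVO | No | Yes | Row 1: same dose |
| Glaucoma | Yes | Yes | Row 2: interrupt, then next lower dose |
| Retinal detachment | Yes | Yes | Row 2: none, or permanent stop (see below) |
| RVO | Yes | Yes | Row 2: none |

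**RVO with ADL-limiting loss.** It meets the row 2 trigger. The interruption is for events other than RVO or detachment, so it does not apply. The stop begins at Grade 3 for RVO, so it does not apply either.

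**Retinal detachment with ADL-limiting loss.** If Grade ≥3 governs both nouns, the result is the same as for RVO. If it governs RVO only, detachment of any grade in that row is a permanent stop. The wording allows both.

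**Count of combinations with no hold or stop in the ocular rows.**
- Grade ≥3 governs RVO only: 3 + 1 = 4 of 6.
- Grade ≥3 governs both: 3 + 2 = 5 of 6.

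**Does text elsewhere close the gap?**
- Section 15.4, opening: the investigator may hold, reduce or stop in any cycle. This permits a hold; it does not direct one.
- Section 15.3, closing text: a DLT may lead to a hold. It is permissive, is limited to Cycle 1 events, and sends the reader back to Table 4.
- Section 12.0: patients may be removed for unacceptable toxicity, with attention to DLTs. No Cycle 1 limit is stated, but this is again permissive and concerns removal.
- Table 4, Other: "Other Grade 2 toxicity that is subjectively intolerable (except alopecia) and not controlled by optimal supportive medication" leads to a hold. The event must be both intolerable and uncontrolled, and it is arguable whether the row reaches an eye event that has rows of its own. Its instruction after resolution is to "restart study treatment at the same dose", which is more lenient than row 2. If it is nevertheless taken to cover the ADL-limiting events, 3 of 6 combinations remain, all of them under row 1's instruction to continue.
- Table 4, Other, last row: recurrent intolerable toxicity leads to the next lower dose and then to discontinuation, but only after interruptions of at least a week on two occasions.

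**The case against.** The strongest reply has five parts.

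1. **DLTs and Table 4 do different jobs.** DLTs drive dose-level decisions and Table 4 manages individual patients. Section 15.3 says only that a DLT may require a hold, and it allows restart at the same dose. This stands: a mismatch between the two lists is not by itself an error. A reader might infer that every DLT must interrupt dosing; the documents do not say so.
2. **Discretion comes first.** Section 15.4 opens with it, and Table 4 is titled a guideline. A reader might infer that the protocol obliges staff to keep dosing a patient with RVO; it does not. Row 1 also requires at least monthly eye examinations. But discretion neither withdraws an explicit instruction to continue nor supplies the missing one for RVO.
3. **CTCAE v5.0 is not in the documents.** The three row 1 combinations matter only if each diagnosis can be Grade 2 without ADL-limiting acuity loss. The general Grade 2 wording in section 15.0 includes limits on instrumental ADL, so those cells may be sparse. This stands as a limit on the row 1 half. The RVO gap in row 2 does not depend on it.
4. **The events are probably rare.** RVO risk factors are screened out in 6.1 and 6.2. Section 3.2 reports predisposing factors in all subjects with RVO, and 4.2 reports no RVO at 4 mg BID intermittent. From 1 to 8 mg BID, section 3.2 reports Grade 1 eye events in two patients, those of one judged unrelated. It also lists one patient with Grade 2 iridocyclitis and Grade 1 subfoveal retinal detachment under 5–8 mg BID, but places those events after escalation to ≥15 mg BID. Against this, one RVO presented after nine cycles in a patient reduced from 10 to 5 mg BID.
5. **The carve-out in row 2 suggests that stricter handling of RVO and detachment was intended.** That is likely, and it is the reason to write it down.

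**Conclusion.** The point holds as a defect in the safety text that should be corrected. Row 1 gives an explicit instruction to continue that exempts none of the three diagnoses. Row 2 states no action for Grade 2 RVO with ADL-limiting loss, on either reading of its last sentence. The surrounding text allows a hold in both situations without requiring one for these diagnoses.

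The 4 of 6 or 5 of 6 count describes coverage of the table. A reader might take it as a measure of patients at risk, but the documents give no frequency for such Grade 2 events. A reader might also infer that retinal detachment certainly shares the RVO gap; that follows only if Grade ≥3 governs both events.

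The conclusion assumes that RVO falls under retinal vascular disorder and, for the row 1 half, that CTCAE v5.0 allows Grade 2 without ADL-limiting loss. No endpoint, sample size or 3+3 rule is affected.

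**What to change.** Amend the ocular rows of Table 4:

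- Exclude RVO and other retinal vascular disorder, retinal detachment and glaucoma from row 1.
- For these events at Grade 2, with or without ADL-limiting acuity loss, interrupt mirdametinib and restart at the next lower dose only after resolution to Grade ≤1.
- For RVO, allow restart only on a documented benefit-risk decision after ophthalmology review; otherwise discontinue permanently. The documents give no basis for making restart the default after RVO.
- State whether Grade ≥3 governs retinal detachment. If a stop at any grade in row 2 was intended for detachment, say so there and let it take precedence over the new Grade 2 rule.

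Leave 15.3 and the 3+3 rules unchanged. Table 5 has no step-down for 3 or 8 mg BID; that is a separate point. The cost is a few lines of amendment text and occasional extra dose holds for Grade 2 events that do not limit ADL.

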6.2 Participant Exclusion Criteria

Subjects are excluded from the study if any of the following criteria apply:

Medical and surgical history

- History of HIV with the following exceptions:
 - Patients with CD4+ T-cell (CD4+) counts \geq 350 cells/uL
- History of AIDS-defining opportunistic infection with the following exceptions:
 - Patients without opportunistic infection within the past 12 months
 - Patients on prophylactic antimicrobials unless the specific antimicrobial drug(s) has an interaction or overlapping toxicity with the proposed treatment as determined by the investigator
- History of active Hepatitis B or Hepatitis C infection at screening with the following exceptions:
 - Patients with Hepatitis B on a suppressive antiviral therapy
 - Patients with Hepatitis C who have completed curative antiviral treatment and have an undetectable viral load
- History (within 5 years) or current evidence of neoplastic disease other than the cancer under study, except cervical carcinoma in situ, superficial noninvasive bladder tumors, curatively treated Stage I-II non-melanoma skin cancer, or any other previous cancer curatively treated <5 years before the start of treatment.

Memorial Sloan Kettering Cancer Center
[name]
[name]

- Current evidence of untreated/unstable symptomatic primary CNS tumor, metastases, leptomeningeal carcinomatosis, or spinal cord compression. Exception: Patients are eligible if neurological symptoms are stable for 14 days prior to the first treatment dose and no CNS surgery or radiation has been performed for 28 days, or 14 days of SRS.
- Current evidence of CTCAE Grade >1 toxicity before the start of treatment, except for hair loss.
 - Subjects with Grade 2 neuropathy may be eligible at the investigator's discretion.
- History or current evidence of ocular abnormalities on ophthalmologic examination that would be considered a risk factor for central serous retinopathy, RVO or neovascular macular degeneration (mild and controlled age-related macular degeneration may be acceptable at the investigator's discretion)
- Current evidence of incomplete recovery from surgery or radiotherapy at screening or planned major surgery or radiotherapy during the treatment. Minor elective surgery may be acceptable at the investigator's discretion.
- History or current evidence of significant (CTCAE Grade ≥ 2) infection or wound within 2 weeks before the start of treatment.

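### The Grade 3 AST/ALT row of Table 4 sets two different re-start grades for patients with liver metastases, and the general rule in Section 15.4 does not reconcile them

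*Combined protocol and SAP*

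**What the plan says.** Section 15.4 sends mirdametinib modification to Tables 4 and 5 and also gives a general rule for ending an interruption. It does not say which prevails if they differ. Four pieces of text bear on this point.

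- **Table 4, AST or ALT.** The row covers "Grade 3 AST or ALT increase (>5.0x to 20.0x ULN if baseline was normal; >5.0x to 20.0x baseline if baseline was abnormal". Its two sentences read "Interrupt mirdametinib until resolution to Grade ≤1 (or Grade ≤2 if the subject has liver metastases). After resolution to Grade ≤1, re-start mirdametinib", the second going on to name the next lower dose in Table 5.
- **General rule, 15.4.** "Treatment should remain interrupted until the AE has resolved to Grade" 1 or less, with Grade 2 accepted for rash. Grade 2 may also be accepted at the Investigator's discretion "if same toxicity was ongoing at Grade 2 since the pre-treatment baseline". Liver metastases are not mentioned.
- **Time limit, 15.4.** Re-start is allowed if satisfactory resolution comes within 21 days. For an event that takes longer than 21 "to reach satisfactory resolution, then the study treatment should be permanently discontinued, unless the Investigator has determined" that the benefit-risk of re-starting is acceptable. The unit is missing from that sentence, but the one before it gives days.
- **Entry limits, 6.1 and 6.2.** AST and ALT may be at most 3.0 times ULN (or 3.0 times an abnormal baseline), labelled CTCAE Grade 1 or less. Section 6.2 excludes "Current evidence of CTCAE Grade >1 toxicity before the start of treatment, except for hair loss", with discretion only for Grade 2 neuropathy.

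**The concern.** The protocol includes a provision for patients with liver metastases, so it expects the case to arise. Both arms enrol metastatic disease, and liver metastases are not an exclusion. Yet the provision appears only in the sentence that ends the interruption. The sentence that permits dosing again does not repeat it. In the muscle-weakness row of the same table, by contrast, the interruption and re-start grades match.

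Safety and tolerability are the primary objectives in both arms. Section 14.3 lists TEAEs leading to study drug discontinuation and TEAEs leading to dose modification among its key safety parameters. If two investigators can follow the text, treat identical patients differently and neither commit a deviation, those counts partly reflect how the row was read.

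**Working it through.** No formula applies and the plan states no figure to reproduce. The check sets the sentences side by side and follows a patient through them.

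**Step 1: where the sentences disagree.** Section 6.1 labels values up to 3.0 times the reference as Grade 1 or less, and Table 4 starts Grade 3 above 5.0 times. Grade 2 is therefore the band above 3.0 and up to 5.0 times ULN, or times baseline if that was abnormal. For a patient with liver metastases in this band, the first sentence of the row ends the interruption and the second does not yet permit re-start.

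**Step 2: whether the general rule settles it.** It requires Grade 1 or less. The rash exception is irrelevant here. The baseline exception needs Grade 2 AST/ALT since before treatment, which the limits in 6.1 and 6.2 almost exclude. The general rule thus agrees with the second sentence and conflicts with the first, and no order of precedence is given.

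**Step 3: the 21-day limit.** Satisfactory resolution is not defined separately for this row, so the two sentences can give two resolution dates. For a patient with liver metastases and a Grade 3 rise on day 0:

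| Course | First sentence followed | Second sentence and general rule followed |
|---|---|---|
| (a) Falls directly to Grade 1 or less by day 21 | Re-start, one step down | Same |
| (b) At Grade 2 on or before day 21 | Re-start, one step down | Interruption continues |
| (c) Grade 2 by day 21, Grade 1 not reached by day 21 | Resolved in time, re-start | Not resolved in time; discontinuation is the default, open to Investigator override |
| (d) Still Grade 3 after day 21 | 21-day rule applies | 21-day rule applies |

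The readings differ in (b) and (c) only, and discontinuation separates them only in (c).

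**Step 4: illustration (assumed course).** ALT falls to Grade 2 on day 10 and stays there. On the first reading, resolution is on day 10, within the limit, and dosing resumes at the lower dose. On the second, the patient stays off drug for a further 21 − 10 = 11 days, after which discontinuation is the default.

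**Step 5: effect on the tabulations.** In (c) the first reading yields a TEAE leading to dose modification. The second yields a TEAE leading to study drug discontinuation, unless overridden. In (b) the event leads to dose modification on either reading while the interruption lasts, but time off drug differs.

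**The case against.** The best defence is that the re-start sentence is stock wording, repeated in the ophthalmological, neurological, muscle-weakness and rash rows. The liver-metastasis parenthesis is the only text specific to this row, and interrupting until Grade 2 already implies resuming at Grade 2. On that view a specific exception governs a generic sentence, and the defect is an incomplete edit. This is a reasonable reading, so it would go too far to say that the exception cannot operate. But the text does not state it, and the general rule points the other way. Read literally, the second sentence leaves the parenthesis with almost no effect.

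It can also be said that Table 4 is titled a guideline and that 15.4 gives the Investigator broad discretion to interrupt, reduce or stop. That stands as a limit on the consequence. It does not make the two sentences agree.

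A reader might infer that the choice of sentence alone decides between re-start and permanent discontinuation. It does not. The Grade 3 row never mentions discontinuation; within the AST/ALT block it is stated only for Grade 4, with a separate row for potential Hy's Law cases. The outcome needs the 21-day rule, a Grade 2 value reached in time, no Grade 1 value by day 21, and no Investigator override.

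**Conclusion.** The point holds as an internal contradiction in an operative rule: two re-start grades for the same patient, with a general rule that supports one and has no exception for the other. Before day 21 the difference is re-start against continued interruption. Past day 21 it becomes re-start against discontinuation by default, subject to Investigator judgement.

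Its size in patients cannot be estimated. The documents give neither the share with liver metastases nor the rate of Grade 3 AST/ALT rises on mirdametinib. A reader might take the statement in Section 15.5 that hepatic enzymes rise in more than 15% of fulvestrant users and apply it to the 60 patients planned for the Arm 1 expansion (0.15 × 60 = 9). That figure does not measure this problem. It includes ALP, gives no grade, concerns fulvestrant and not mirdametinib-related events, and is not limited to patients with liver metastases. The 0.4% discontinued for elevated liver enzymes on fulvestrant in the same section is not a Grade 3 rate either.

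A reader might also infer a direct effect on CBR, DOR or PFS. Section 13.4.2 continues scans after discontinuation for reasons other than progression, until progression or new anticancer treatment, and Section 14.5 does not censor PFS or DOR at treatment stop. Any efficacy effect is at most indirect, through exposure.

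The conclusion rests on the wording of the row and of 15.4, and on reading the bare 21 as days.

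**What to change.** Reconcile the two sentences of the Grade 3 AST/ALT row with each other and with the resolution rule in 15.4. State a single re-start grade for patients with liver metastases, and state that the same grade counts as satisfactory resolution for the 21-day limit. Supplying the missing unit in the 21-day sentence can be done at the same time. Which grade applies is for the sponsor and investigators to decide. The cost is one sentence in Table 4 and a matching clause in 15.4, with no new visits, data or analyses.
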